#### **4.3.9 Safety Analysis**

##### **Adverse Events:**

All analyses will be conducted in the safety population. Adverse events will be recorded from the time of consent until completion of study. The number and percentage of subjects with AEs will be displayed by body system and preferred term (MedDRA), by study treatment. Summaries in terms of severity and relationship to Study Drug will also be provided. All SAEs will be summarized in a similar manner. Participant listings of all AEs causing discontinuation of study medication and SAEs will be produced.

All AEs will be listed for individual subjects showing both verbatim and preferred terms. Separate summaries of treatment emergent SAEs and TEAEs related to Study Drug will be generated.

AEs will be summarized separately during the CRC treatment visits. Any AE that occurs after administration of study drug at Visit 3 and prior to administration of the alternate study drug at Visit 4 will be treatment emergent with respect to the study drug received at Visit 3. Any AE that occurs after administration of study drug at Visit 4 and prior to the first administration of study drug in the out-patient phase will be treatment emergent for the study drug received at Visit 4. Any event reported on the eCRF that occurs at the time of or after the initiation of Study Drug in the out-patient phase is defined as treatment-emergent for that study drug. Additionally, an AE that was reported to have started on Day 1 without an associated onset time is assumed to have

occurred after the initiation of Study Drug. Hence, AEs occurring on Day 1 with no associated onset time are assumed to be treatment emergent.

SAEs associated with a protocol specified procedure and occurring after the time of consent but before administration of first dose of Study Drug are defined as Non-Treatment Emergent AEs (NTEAE).

### **Physical Examination:**

All physical examination findings will be provided in the listings.

### **12-Lead ECG:**

ECG results will be summarized using frequency counts for Overall Evaluation (normal, abnormal NCS, and abnormal CS) by treatment for Screening and EOS using Safety Population.

All ECG data will be listed for each subject with abnormal values flagged in the listing.

### **Vital Signs:**

Vital signs (systolic and diastolic blood pressure, heart rate, respiratory rate, temperature) will be summarized using the descriptive statistics for each vital sign measurement and change from baseline by treatment and timepoint for CRC phase and Outpatient phase using the Safety Population.

Vital Sign data will be listed by timepoint for each parameter and subject by treatment.

### **Laboratory:**

Laboratory evaluation results for observed values and change from baseline will be summarized descriptively by treatment and visit using Safety Population. Unless otherwise specified, all continuous laboratory data will be summarized using descriptive statistics (n, mean, SD, median, min, and max) for each scheduled study assessment as well as change from baseline by parameter class (Hematology and Biochemistry). Abnormal laboratory values will be summarized using frequency and percentage using the safety population.

Hematology and Chemistry data will be summarized by displaying shifts from baseline value (low/normal/high or Normal/Abnormal as applicable) to subsequent assessment.

Safety laboratory data (Hematology and Chemistry) will be listed by timepoint for each parameter and subject. All abnormal values will be flagged on the listing. Serology, HbA1c and C-peptide data will also be listed.

#### **Draize Scales, Injection Site Discomfort and Duration Questionnaire:**

Erythema formation, Edema formation and Injection Site Discomfort data will be summarized at CRC phase using Safety population.

The Injection Site Discomfort Description and Duration Questionnaire is a 3-question instrument that assesses a subject's level of discomfort and its duration post-injection. There are 5 responses for each of the first 2 questions, which address the level of discomfort and the duration of the discomfort, respectively, for each injection. For the 3rd question, the total time for the duration of discomfort is to be provided.

All categorical data will be summarized by using and frequency and percentage and continuous data will be summarized using descriptive statistics.

#### **4.3.10 Immunogenicity**

Details and results for immunogenicity sample analysis will be provided in a separate analysis document.

#### **4.3.11 Interim Analysis**

There are no planned interim analyses for this study.

### **4.4 CHANGES FROM PROTOCOL**

NA

### **4.5 REFERENCES**

NA

### **4.6 APPENDICES**

#### **4.6.1 APPENDIX 1. Example of SAS syntax code for primary endpoint analysis.**

The following SAS syntax code can be referred to during programming of primary endpoint analysis:

```
PROC ANOVA DATA = clover;
  CLASS trt_o;
  MODEL param = trt_o;
RUN;
```

Alternative:

```
PROC GLM DATA = xx;
  CLASS trt_o;
  MODEL param = trt_o/ ss3;
  LSMEANS trt_o / PDIFF CL ALPHA=0.05;
RUN;
```

Alternative:

```
PROC MIXED DATA=school METHOD=type3;
  CLASS trt_o;
  MODEL param= trt_o;
RUN;
```

The following SAS syntax example code can be referred to during testing the normality of the residuals using the Shapiro-Wilk W-test.

```
PROC UNIVARIATE DATA=xxxxx NORMAL PLOT;
  VAR yyyy;
  QQPLOT yyyy /NORMAL (MU=EST SIGMA=EST COLOR=RED L=1);
RUN;
```

#### 4.6.2 APPENDIX 2. Example of SAS syntax code for secondary endpoint analysis.

The following macro can be used for the calculation of area over the curve (AOC):

```
%macro auc (dsn);
  data auctree;
    set &dsn;
    if concentration = 0 and time > tlast then delete;
    x = time;
    y = concentration;
    xpre = lag(x);
    ypre = lag(y);
    xdif = x - xpre;
    if x <= tmax or y = ypre or y =0 or ypre = 0 then do;
      auc = xdif * (( y + ypre ) / 2 );*linear rule;
    end;
    else do;
      auc = xdif * ((y - ypre) / log (y / ypre));
    end;
  run;
```

```

      end;
run;

proc summary data = auctree noprint;
  var auc;
  output out = aucest sum = auCL;
run;

proc sort data = auctree out = part1 nodupkey ;
  by subject ;
run;
data AUCs&i (keep = subject period auCL);
  merge part1 aucest;
run;
%mend auc;

```

The following macro can be used to perform estimation according to Trapezoidal Rule:

```

%macro trap(a,b,n, function);
  data f1;
    do i = 0 to &n ;
      if i = 0 then do;
        x = &a ;
        y = ((&b - &a)/&n )*( &function / 2 );
        output;
      end;
      else if i = &n then do;
        x = &b ;
        y = ((&b - &a)/&n )*( &function / 2 );
        output;
      end;
      else do;
        x = ( &a + i * (( &b - &a) / &n ) );
        y = ((&b - &a) / &n) * &function;
        output;
      end;
    end;
  end;
run;
proc summary data=f1;
  var y;
  output out=p1 sum=areau;run;
proc print data=p1;
run;
%mend;

```

The Chi-Square/Fisher's exact test can be done using the following SAS code example:

```

PROC FREQ DATA = data;
  TABLES param*trt / CHISQ FISHER EXPECTED;

```

```
WEIGHT count;
RUN;
```

Kruskal Wallis test can be performed in SAS using the following reference code:

```
PROC NPAR1WAY DATA=soil WILCOXON;
  CLASS location;
  EXACT WILCOXON / MC;
  VAR claypct;
RUN;
```

T test within the cross over design in CRC phase can be done with the help of the following reference code:

```
PROC TTEST DATA=data PLOTS=interval;
  VAR aval1 aval2 / CROSSOVER = (TrtA TrtB);
RUN;
```

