5.2.2. Key Secondary Endpoints

- Glucose levels below target range, measured by unblinded CGM (inpatient and outpatient), defined as both time (in minutes) and mean decremental area over the curve (AUC(0-300 min) in minutes*mg/dL) during exercise:
 - • Below range, as defined by interstitial glucose (IG) \leq 70 mg/dL (\leq 3.89 mmol/L)
 - • Below range, as defined by IG between 54 to 70 mg/dL (3 – 3.89 mmol/L)
 - • Below range, as defined by IG $<$ 54 mg/dL ($<$ 3 mmol/L)
 - • Proportional time (percentage time within hypoglycemia IG \leq 70 mg/dL (3.89 mmol/L) and clinically significant hypoglycemia IG $<$ 54 mg/dL (3 3 mmol/L))
- Insulin utilization as reported by the subject at Baseline, Weeks 4, 8, and 12 in the Outpatient Phase.
- Change from Baseline to the end of the Outpatient Phase in PROs: Barriers to Physical Activity in Diabetes (Type 1) (BAPAD-1), Hypoglycemia Fear Survey (HFS-II), and Hypoglycemic Confidence Scale (HCS),

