#### Secondary Endpoints:

1. Interstitial glucose (IG) levels below target range, measured by unblinded CGM (inpatient and outpatient), defined as both time (in minutes) and mean decremental area over the curve (AOC (0-300 min) in minutes\*mg/dL) during exercise:
  - Below range, as defined by  $IG \leq 70 \text{ mg/dL} (\leq 3.89 \text{ mmol/L})$

- Below range, as defined by IG between 54 to 70 mg/dL (3–3.89 mmol/L)
- Below range, as defined by IG < 54 mg/dL (<3 mmol/L)
- Proportional time (percentage time within hypoglycemia IG  $\leq$  70 mg/dL (3.89 mmol/L) and clinically significant hypoglycemia IG < 54 mg/dL (3mmol/L)).

2. Insulin utilization as reported by subject at baseline, and weeks 4, 8 and 12 in the outpatient setting.
3. Change from Baseline to the end of the Outpatient Phase in PROs: Barriers to Physical Activity in Diabetes (Type 1) (BAPAD-1), Hypoglycemia Fear Survey (HFS-II), and Hypoglycemic Confidence Scale (HCS).

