#### **4.3.7 Secondary Endpoint Analysis:**

Glucose levels below target range will be measured and analyzed as the mean decremental area over the curve (AOC(0-5hrs) in minutes\*mg/dL) during exercise. AOC will be estimated using Trapezoidal Rule.

Analysis will be conducted for glucose levels below range (interstitial glucose  $\leq 70$  mg/dL (3.89 mmol/L), interstitial glucose between 54-70 mg/dL (3 – 3.89 mmol/L),  $<54$  mg/dL (3 mmol/L)) using a contingency table and treatment difference will be calculated using Chi square/Fisher's exact test.

Proportional time (percentage within serious hypoglycemia <54 mg/dL (3 mmol/L)) will be calculated and treatment difference will be calculated using ANOVA/Kruskal–Wallis test, based on whether the data is normally distributed or not respectively.

Insulin utilization as reported by subjects in Outpatient phase and change from baseline will be analyzed using ANOVA.

The Questionnaires will be analyzed using T Test/ANOVA for CRC/outpatient phase. For ANOVA, significant value will lead to a post hoc analysis for identifying the treatment pairs which are significantly different.

Changes from baseline in questionnaire values (numeric) will be analyzed by the ANCOVA model using treatment arm at Outpatient phase, treatment sequence in CRC phase, sex as factors with age, weight and baseline value as covariates.

Example of SAS syntax code that can be used for secondary endpoint analysis is provided in APPENDICES 2.

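### The example macro in SAP Appendix 2 for the CGM area over the curve computes total area under the raw glucose curve, so it does not match the below-range measure it is offered for

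*SAP*

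**What the plan says.** Protocol 5.2.2 places this measure among the key secondary endpoints: "Glucose levels below target range, measured by unblinded CGM (inpatient and outpatient". SAP Section 3 lists it under secondary endpoints, "defined as both time (in minutes) and mean decremental area over the curve", over 0-300 minutes and in minutes*mg/dL. It is wanted for three ranges: at or below 70 mg/dL; "Below range, as defined by IG between 54 to 70 mg/dL (3–3.89 mmol/L"; and "Below range, as defined by IG < 54 mg/dL (<3 mmol/L".

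SAP 4.3.7 repeats the intention: "Glucose levels below target range will be measured and analyzed as the mean decremental area over the curve". On the arithmetic it adds only "AOC will be estimated using Trapezoidal Rule". Neither section states the reference line, the subtraction or what happens when glucose is above the line.

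SAP 4.6.2 (Appendix 2) then gives example code, introduced by "The following macro can be used for the calculation of area over the curve (AOC". The macro sets y to the variable `concentration`, forms an area for each interval and sums the intervals. A linear rule applies under the condition "if x <= tmax or y = ypre or y =0 or ypre = 0 then do", and a logarithmic rule applies otherwise. A second macro in the same appendix is a generic linear trapezoid for a function that the user supplies. It carries no limit either.

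**The concern.** A decremental area below a limit should be zero in a session that never goes low, and should grow with the depth and duration of the low. The macro labelled for this purpose has no limit, no subtraction and no truncation at zero. Its variables (`concentration`, `tmax`, `tlast`) and its logarithmic branch belong to a drug-concentration AUC. What it integrates is the whole glucose curve down to zero.

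A programmer who follows it would report, under a below-range title, a number that mostly reflects average glucose. If the fault is noticed only after treatment codes are known, the formula for an endpoint that the protocol calls key secondary would be chosen post hoc.

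**Working it through.** **Inputs.** The limits (70 and 54 mg/dL) and the window (0-300 min) come from SAP Section 3, and the macro's rules from Appendix 2. The documents contain no glucose curves, so the profiles below are assumptions: readings every 5 minutes, in mg/dL, with straight lines between the breakpoints shown. The plan states no figure to reproduce.

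**Formulas.**
- Macro, per interval of width d with readings y0 and y1: d × (y0 + y1)/2 up to tmax (or if the readings are equal or one is zero); otherwise d × (y1 - y0)/ln(y1/y0). The intervals are summed. tmax is taken as the time of the highest reading, and the macro is applied to one session at a time.
- Intended area below limit L: the integral over 0-300 min of max(0, L - IG).

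**By hand.** Constant 140: macro 140 × 300 = 42,000; area below 70 = 0. Constant 60: macro 60 × 300 = 18,000; area below 70 = (70 - 60) × 300 = 3,000.

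**Results (minutes*mg/dL).**

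| Profile (minute: mg/dL) | Macro | Area below 70 | Area below 54 |
|---|---|---|---|
| Constant 180 | 54,000 | 0 | 0 |
| Constant 120 | 36,000 | 0 | 0 |
| Constant 100 | 30,000 | 0 | 0 |
| Dip to 75 (0:120, 45:80, 75:75, 120:100, 300:120) | 30,561 | 0 | 0 |
| Dip to 50 (0:120, 45:65, 75:50, 120:110, 300:120) | 30,183 | 535 | 22 |
| Long dip to 45 (0:120, 45:60, 75:45, 150:50, 200:100, 300:120) | 23,934 | 2,450 | 577 |
| Dip to 50, rebound to 260 (0:120, 45:65, 75:50, 120:180, 180:260, 300:220) | 53,062 | 454 | 19 |

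**What the table shows.**
1. Sessions with no low score 30,000 to 54,000 instead of 0.
2. With the rest of the curve unchanged, lower glucose gives a smaller value, because both the linear and the logarithmic interval areas fall when a reading falls.
3. Glucose above the low range dominates. The two dips to 50 have similar true areas (535 and 454), but their macro values differ by 53,062 - 30,183 = 22,879. Going from the dip to 75 to the dip to 50 changes the macro by only 30,561 - 30,183 = 378.
4. No limit enters the code, so a session has one macro value for all three bands.

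**Size of the logarithmic rule.** For the dip to 50, linear trapezoids give 45 × 92.5 + 30 × 57.5 + 45 × 80 + 180 × 115 = 30,187.5, against 30,183 from the macro. The rule departs from 4.3.7, but here it is numerically minor. The missing limit is the real fault.

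**Units.** SAP 4.3.2 stores CGM values in mmol/L, while the endpoint is in minutes*mg/dL. The documents equate 180 mg/dL with 10 mmol/L, a factor of 18. The macro has no conversion, so on stored values a constant 60 mg/dL would return 18,000/18 = 1,000.

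**The 54-70 band.** Two definitions are possible, and they differ. For the long dip to 45, the difference of the two areas is 2,450 - 576.5 = 1,873.5. That difference credits 70 - 54 = 16 mg/dL for each of the 97 minutes below 54, or 1,552. The area of 70 - IG over time actually inside the band is 1,873.5 - 1,552 = 321.5. A session constant at 50 mg/dL is never in the band, yet the difference gives 16 × 300 = 4,800.

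**The case against.** The strongest reply is that this is example code with permissive wording, in an appendix of visibly generic templates, and that the body text names the right concept. That stands, and it lowers the severity. A programmer could also pass max(0, 70 - IG) to the macro. For the three profiles that go low, this gives 534.5, 2,451.3 and 457.8 against 535.2, 2,450.0 and 454.5 (leaving aside the macro's line that drops zeros after `tlast`). But no section says to do this, and neither 4.3.7 nor the second macro supplies a limit. The body text does not repair the code.

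Three stronger readings are tempting, and the documents do not support them.

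- **The glucagon arms would be shown as having more hypoglycemia.** The code cannot give a per-session area without rewriting. Its summary step has no grouping by subject or period, the lag runs across subjects, and `tmax`, `tlast` and `&i` are not defined in it. A never-low session scoring tens of thousands would also be conspicuous. Silent reversal of a treatment conclusion is conjecture.
- **The macro ranks sessions in exactly reverse order.** It does not always. The dip with rebound scores 53,062, above constant 120 at 36,000, although only the former contains a low.
- **The macro also spoils the areas above 180 and 250 mg/dL.** It is offered only for the area over the curve. Those areas are exploratory, and SAP 4.3.8 points to Appendix 3, which has no area macro.

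**Conclusion.** The macro and the endpoint do not match. The code labelled as area over the curve returns the full area under the glucose curve, gives large values where the intended measure is zero, and cannot separate the three bands. Used as written on a single session, it does not measure hypoglycemia. This is an error in the supplied code, made worse by the absence of a formula in 4.3.7.

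The reach is limited. The primary BGM endpoint does not use the macro, nor do the contingency-table analysis of the below-range categories or the analysis of proportional time in 4.3.7. That section names no test for the area itself. The sizes above rest on invented profiles, readings in mg/dL and session-by-session application. The absence of a limit does not depend on those assumptions. This should be fixed before unblinding.

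**What to change.** Replace the first macro in Appendix 2 and state the formula in SAP 4.3.7:

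- Convert CGM readings from mmol/L to mg/dL.
- For each subject and session, apply the linear trapezoidal rule over 0-300 minutes to max(0, 70 - IG) for the range at or below 70, and to max(0, 54 - IG) for the range below 54.
- For the 54-70 band, integrate 70 - IG only over time with IG between 54 and 70. If the difference of the two areas is preferred, label it as the area between the 54 and 70 lines and say that it also counts time below 54.
- State that the value is zero without a low and that larger means more or deeper hypoglycemia.

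The cost is a few lines of code and a short paragraph in the SAP. No new data are needed.

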#### 4.6.3 APPENDIX 3. Example of SAS syntax code for exploratory analysis.

The ANCOVA model can be analyzed using the following SAS code example:

```
PROC MIXED DATA=XXXX;
  CLASS SUBJECT TREATMENT trtSEQ sex;
  MODEL &par= TREATMENT trtSEQ sex age weight/DDFM=SATTERTH;
  RANDOM SUBJECT (SEQ);
  REPEATED / GROUP=TREATMENT SUB=SUBJECT R;
  LSMEANS TREATMENT / CL;
  LSMESTIMATE TREATMENT 'Treatment A vs. Treatment B' 1 1 0 /
  CL ALPHA=0.025 E LOWER;
RUN;
```

### 5. LIST OF TABLES, LISTINGS AND FIGURES

The following is the list of anticipated Tables, Listings and Figures for the study. Modifications may be made to this list to follow the SAP and for revisions with the Sponsor. If any new endpoints or new analyses are requested, they will be evaluated for whether an Amendment to the SAP is required.

#### 5.1 Summary Tables

Number	Title
Table 14.1.1.1	Summary of Subject Disposition for CRC Phase All Screened Subjects
Table 14.1.1.2	Summary of Subject Disposition for Outpatient Phase All Screened Subjects
Table 14.1.2.1.1	Summary of Demographic and Baseline Characteristics for CRC Phase

Number	Title
	Safety Population
Table 14.1.2.1.2	Summary of Demographic and Baseline Characteristics for Outpatient Phase Safety Population
Table 14.1.3.1	Summary of Medical History Safety Population
Table 14.1.6.1	Summary of Protocol Deviations at CRC Phase ITT Population
Table 14.1.6.2	Summary of Protocol Deviations at CRC Phase Safety Population
Table 14.1.6.3	Summary of Protocol Deviations at Outpatient Phase ITT Population
Table 14.1.6.4	Summary of Protocol Deviations at Outpatient Phase Safety Population
Table 14.2.1.1.1	Mean Incidence Rate of Hypoglycemia at CRC Phase ITT Population
Table 14.2.1.1.2	Mean Incidence Rate of Hypoglycemia at CRC Phase PP Population
Table 14.2.1.1.3	Summary of Percent Change from baseline in the 80% target heart rate reached at least once during the qualified exercise session CRC Phase ITT Population
Table 14.2.1.1.4	Summary of Percent Change from baseline in the 80% target heart rate reached at least once during the qualified exercise session CRC Phase PP Population
Table 14.2.1.2.1	Mean Incidence Rate of Hypoglycemia at Outpatient Phase ITT Population
Table 14.2.1.2.2	Mean Incidence Rate of Hypoglycemia at Outpatient Phase PP Population
Table 14.2.1.2.3	Summary of Percent Change from baseline in the 80% target heart rate reached at least once during the qualified exercise session Outpatient Phase ITT Population
Table 14.2.1.2.4	Summary of Percent Change from baseline in the 80% target heart rate reached at least once during the qualified exercise session Outpatient Phase PP Population
Table 14.2.2.1.1	Summary of Insulin Utilization at Outpatient Phase ITT Population
Table 14.2.2.1.2	Summary of Insulin Utilization at Outpatient Phase PP Population
Table 14.2.2.2.1	Summary of BAPAD-1 score for Outpatient Phase ITT Population
Table 14.2.2.2.2	Summary of BAPAD-1 score for Outpatient Phase PP Population
Table 14.2.2.3.1	Summary of HFS-II score for Outpatient Phase ITT Population
Table 14.2.2.3.2	Summary of HFS-II score for Outpatient Phase PP Population
Table 14.2.2.4.1	Summary of HCS score for Outpatient Phase ITT Population
Table 14.2.2.4.2	Summary of HCS score for Outpatient Phase PP Population
Table 14.2.3.1.1.1	Summary of Overnight Hypoglycemia at CRC Phase ITT Population
Table 14.2.3.1.1.2	Summary of Overnight Hypoglycemia at CRC Phase PP Population
Table 14.2.3.1.2.1	Summary of Incidence of Overnight Hypoglycemia at CRC Phase ITT Population
Table 14.2.3.1.2.2	Summary of Incidence of Overnight Hypoglycemia at CRC Phase PP Population
Table 14.2.3.2.1.1	Summary of Overnight Hypoglycemia at Outpatient Phase ITT

Number	Title
	Population
Table 14.2.3.2.1.2	Summary of Overnight Hypoglycemia at Outpatient Phase PP Population
Table 14.2.3.2.2.1	Summary of Incidence of Overnight Hypoglycemia at Outpatient Phase ITT Population
Table 14.2.3.2.2.2	Summary of Incidence of Overnight Hypoglycemia at Outpatient Phase PP Population
Table 14.2.3.3.1.1	Summary of Glucose Tablet Usage at CRC Phase ITT Population
Table 14.2.3.3.1.2	Summary of Glucose Tablet Usage at CRC Phase PP Population
Table 14.2.3.3.2.1	Summary of Glucose Tablet Usage at Outpatient Phase ITT Population
Table 14.2.3.3.2.2	Summary of Glucose Tablet Usage at Outpatient Phase PP Population
Table 14.2.3.4.2.1	Summary of Changes in Weight at Outpatient Phase ITT Population
Table 14.2.3.4.2.2	Summary of Changes in Weight at Outpatient Phase PP Population
Table 14.2.3.5.2.1.1	Summary of Exercise Sessions completed at Outpatient Phase ITT Population
Table 14.2.3.5.2.1.2	Summary of Exercise Sessions by subgroup at Outpatient Phase ITT Population
Table 14.2.3.5.2.2.1	Summary of Exercise Sessions completed at Outpatient Phase PP Population
Table 14.2.3.5.2.2.1	Summary of Exercise Sessions by subgroup at Outpatient Phase PP Population
Table 14.2.3.6.2.1	Summary of Number of Minutes Exercised per week at Outpatient Phase ITT Population
Table 14.2.3.6.2.2	Summary of Number of Minutes Exercised per week at Outpatient Phase PP Population
Table 14.2.3.7.2.1	Summary of Number of Calories Burned per Exercise sessions at Outpatient Phase ITT Population
Table 14.2.3.7.2.2	Summary of Number of Calories Burned per Exercise Sessions at Outpatient Phase PP Population
Table 14.2.3.8.2.1	Summary of Number of Steps, Distance achieved During Exercise Sessions at Outpatient Phase ITT Population
Table 14.2.3.8.2.2	Summary of Number of Steps, Distance achieved During Exercise Sessions at Outpatient Phase PP Population
Table 14.2.3.9.1.1	Summary of Mean Carbohydrate Intake at Outpatient Phase ITT Population
Table 14.2.3.9.1.2	Summary of Mean Carbohydrate Intake at Outpatient Phase PP Population
Table 14.2.3.9.2.1	Summary of Carbohydrate Intake by Hypoglycaemic Events at Outpatient Phase ITT Population
Table 14.2.3.9.2.2	Summary of Carbohydrate Intake by Hypoglycaemic Events at Outpatient Phase PP Population
Table 14.2.3.10.1.1	Summary of Heart Rate at CRC Phase ITT Population

Number	Title
Table 14.2.3.10.1.2	Summary of Heart Rate at CRC Phase PP Population
Table 14.2.3.10.2.1	Summary of Heart Rate at Outpatient Phase ITT Population
Table 14.2.3.10.2.2	Summary of Heart Rate at Outpatient Phase PP Population
Table 14.2.3.11.1.1	Summary of Daily Assessments at CRC Phase ITT Population
Table 14.2.3.11.1.2	Summary of Daily Assessments at CRC Phase PP Population
Table 14.2.3.11.2.1	Summary of Daily Assessments at Outpatient Phase ITT Population
Table 14.2.3.11.2.2	Summary of Daily Assessments at Outpatient Phase PP Population
Table 14.2.3.12.1.1	Summary of HbA1c ITT Population
Table 14.2.3.12.1.2	Summary of HbA1c PP Population
Table 14.2.4.1.1	Analysis of Incidence of Hypoglycemia at CRC Phase ITT Population
Table 14.2.4.1.2	Analysis of Incidence of Hypoglycemia CRC Phase PP Population
Table 14.2.4.1.3	Analysis of Incidence of Hypoglycemia at Outpatient Phase ITT Population
Table 14.2.4.1.4	Analysis of Incidence of Hypoglycemia Outpatient Phase PP Population
Table 14.2.4.2.1	Analysis of Change from baseline in BAPAD-1 score at Outpatient Phase ITT Population
Table 14.2.4.2.2	Analysis of Change from baseline in BAPAD-1 score at Outpatient Phase PP Population
Table 14.2.4.3.1	Analysis of Change from baseline in HFS-II score at Outpatient Phase ITT Population
Table 14.2.4.3.2	Analysis of Change from baseline in HFS-II score at Outpatient Phase PP Population
Table 14.2.4.4.1	Analysis of Change from baseline in HCS score at Outpatient Phase ITT Population
Table 14.2.4.4.2	Analysis of Change from baseline in HCS score at Outpatient Phase PP Population
Table 14.2.4.5.1.1	Analysis of Interstitial Glucose (IG) below Target Range at CRC Phase ITT Population
Table 14.2.4.5.1.2	Analysis of Interstitial Glucose (IG) below Target Range at CRC Phase PP Population
Table 14.2.4.5.2.1	Analysis of Interstitial Glucose (IG) below Target Range at Outpatient Phase ITT Population
Table 14.2.4.5.2.2	Analysis of Interstitial Glucose (IG) below Target Range at Outpatient Phase PP Population
Table 14.2.4.5.3.1	Analysis of Time within Hypoglycemia at CRC Phase ITT Population
Table 14.2.4.5.3.2	Analysis of Time within Hypoglycemia at CRC Phase PP Population
Table 14.2.4.5.4.1	Analysis of Time within Hypoglycemia at Outpatient Phase ITT Population
Table 14.2.4.5.4.2	Analysis of Time within Hypoglycemia at Outpatient Phase PP Population
Table 14.2.4.5.5.1	Analysis of Interstitial Glucose (IG) within Target Range at CRC

Number	Title
	Phase ITT Population
Table 14.2.4.5.5.2	Analysis of Interstitial Glucose (IG) within Target Range at CRC Phase PP Population
Table 14.2.4.5.6.1	Analysis of Interstitial Glucose (IG) above Target Range at CRC Phase ITT Population
Table 14.2.4.5.6.2	Analysis of Interstitial Glucose (IG) above Target Range at CRC Phase PP Population
Table 14.2.4.5.7.1	Analysis of Interstitial Glucose (IG) above Target Range at Outpatient Phase ITT Population
Table 14.2.4.5.7.2	Analysis of Interstitial Glucose (IG) above Target Range at Outpatient Phase PP Population
Table 14.3.1.1.1	Overall Summary of Adverse Events at CRC Phase Safety Population
Table 14.3.1.1.2	Overall Summary of Adverse Events at Outpatient Phase Safety Population
Table 14.3.1.2.1	Summary of Treatment Emergent Adverse Events by MedDRA System Organ Class and Preferred Term at CRC Phase Safety Population
Table 14.3.1.2.2	Summary of Treatment Emergent Adverse Events by MedDRA System Organ Class and Preferred Term at Outpatient Phase Safety Population
Table 14.3.1.3.1	Summary of Serious Adverse Events by MedDRA System Organ Class and Preferred Term at CRC Phase Safety Population
Table 14.3.1.3.2	Summary of Serious Adverse Events by MedDRA System Organ Class and Preferred Term at Outpatient phase Safety Population
Table 14.3.1.4.1	Summary of Treatment-Emergent Serious Adverse Events by MedDRA System Organ Class and Preferred Term at CRC Phase Safety Population
Table 14.3.1.4.2	Summary of Treatment-Emergent Serious Adverse Events by MedDRA System Organ Class and Preferred Term at Outpatient Phase Safety Population
Table 14.3.1.5.1	Summary of Treatment-Emergent Adverse Events by Highest Severity, MedDRA System Organ Class and Preferred Term for CRC Phase Safety Population
Table 14.3.1.5.2	Summary of Treatment-Emergent Adverse Events by Highest Severity, MedDRA System Organ Class and Preferred Term for Outpatient Phase Safety Population
Table 14.3.1.6.1	Summary of Treatment-Emergent Adverse Events by System Organ Class, Preferred Term, Relationship to Study Drug and by Treatment at CRC Phase Safety Population
Table 14.3.1.6.2	Summary of Treatment-Emergent Adverse Events by System Organ Class, Preferred Term, Relationship to Study Drug and by Treatment at Outpatient Phase Safety Population
Table 14.3.1.7.1	Summary of Deaths due to Treatment-Emergent Adverse Events at

Number	Title
	CRC Phase Safety Population
Table 14.3.1.7.2	Summary of Deaths due to Treatment-Emergent Adverse Events at Outpatient Phase Safety Population
Table 14.3.1.8.1	Summary of Treatment-Emergent Adverse Events Leading to Study Discontinuation by MedDRA System Organ Class and Preferred Term at CRC Phase Safety Population
Table 14.3.1.8.2	Summary of Treatment-Emergent Adverse Events Leading to Study Discontinuation by MedDRA System Organ Class and Preferred Term at Outpatient Phase Safety Population
Table 14.3.2.1	Listing of Deaths at CRC Phase Safety Population
Table 14.3.2.2	Listing of Deaths at Outpatient Phase Safety Population
Table 14.3.2.3	Listing of Serious Adverse Events at CRC Phase Safety Population
Table 14.3.2.4	Listing of Serious Adverse Events at Outpatient Phase Safety Population
Table 14.3.2.5	Listing of Treatment-Emergent Adverse Events leading to Premature Discontinuation of Study Drug at CRC Phase Safety Population
Table 14.3.2.6	Listing of Treatment-Emergent Adverse Events leading to Premature Discontinuation of Study Drug at Outpatient Phase Safety Population
Table 14.3.4.1.1	Summary of Vital Signs at CRC Phase Safety Population
Table 14.3.4.1.2	Summary of Vital Signs at Outpatient Phase Safety Population
Table 14.3.4.2.1	Summary of Laboratory Data – Hematology Safety Population
Table 14.3.4.2.2	Summary of Laboratory Data – Clinical Chemistry Safety Population
Table 14.3.4.2.3	Summary of Abnormal Laboratory Findings Safety Population
Table 14.3.4.3.1	Summary of 12 Lead ECG Findings Safety Population
Table 14.3.4.3.2	Summary of Draize Scales at CRC Phase Safety Population
Table 14.3.4.3.3	Summary of Injection Site Discomfort and Duration at CRC Phase Safety Population
Table 14.3.4.4.1	Summary of Observed Laboratory Data: Shift from Baseline – Hematology Safety Population
Table 14.3.4.4.2	Summary of Observed Laboratory Data: Shift from Baseline – Clinical Chemistry Safety Population

